# 2.4.4.3 Multiplicity issues

Not Applicable.

Property of the Sanofi Group - strictly confidential

# 2.4.4.4 Additional efficacy analysis(es)

Analyses on calculated LDL-C described above may be performed by device in case different devices are used for investigational treatment, in order to assess the impact of the device on study results. Patients will belong to the device they received longer.

# 2.4.5 Analyses of safety data

Unless otherwise specified, safety analyses will be presented overall as well as separately according to treatment (placebo versus alirocumab (regardless of dose)) received in the parent study.

For laboratory parameters and vital signs, analyses of the change from baseline, PCSA according to the baseline status and analyses of PCSA based on change from baseline values, will be performed using the parent baseline and the OLE baseline.

#### General common rules

All safety analyses will be performed on the safety population as defined in Section 2.3.2, unless otherwise specified, using the following common rules:

- The parent baseline value is defined as the last available value obtained up to the date and time of the first double-blind IMP injection in the parent study.
- The OLE baseline is defined as the last available value obtained up to the date and time of the first OLE IMP injection.
- PCSA values are defined as abnormal values considered medically important by the Sponsor according to predefined criteria/thresholds based on literature review and defined by the Sponsor for clinical laboratory tests, vital signs, and ECG (PCSA version dated January 2009 [Appendix A]). Considering that the threshold defined in the PCSA list for monocytes and basophils can be below the ULN, the following PCSA criterion will be used for the PCSA analysis:
  - PCSA criterion for monocytes: >0.7 Giga/L or > ULN (if ULN ≥0.7 Giga/L)
  - PCSA criterion for basophils: >0.1 Giga/L or > ULN (if ULN ≥0.1 Giga/L)
- PCSA criteria will determine which patients had at least 1 PCSA during the TEAE period, taking into account all evaluations performed during the TEAE period, including nonscheduled or repeated evaluations.
- The treatment-emergent PCSA denominator for a given parameter will be based on the number of patients assessed for that given parameter at least once during the TEAE period.
- All measurements, scheduled or unscheduled, fasting or not fasting, will be assigned to analysis windows defined in Section 2.5.4, Table 1 in order to provide an assessment for all planned time points.
- For quantitative safety parameters based on central laboratory/reading measurements, descriptive statistics will be used to summarize results and change from baseline values by

visit using analysis windows. Summaries will also include the last on-treatment value and the worst on-treatment value. The last on-treatment value is defined as the last value collected during the treatment period (see Section 2.1.4). The worst on-treatment value is defined as the nadir and /or the peak value during the treatment period according to the direction (minimum or maximum) of the abnormality as defined in the PCSA list.

Analyses performed according to diabetes status at OLE baseline will be done considering diabetic patients as patients with either type 1 or type 2 diabetes (see selection below) (regardless of the ongoing status) reported in at least one of the following e-CRF pages: medical history of the parent study, AE of the parent study and AE of the current study (selecting pre-treatment AEs only).

Diabetes mellitus events from medical history of the parent study selected using a company MedDRA query (CMQ), based on the following PTs: "diabetes mellitus", "diabetes mellitus inadequate control", "fulminant type 1 diabetes mellitus", "insulin resistant diabetes", "insulin-requiring type 2 diabetes mellitus", "type 1 diabetes mellitus", "type 2 diabetes mellitus", "diabetes mellitus malnutrition-related", and "diabetes mellitus management", will be combined with AEs of the parent study and pre-treatment AEs of the current study selected using primary and secondary HLGT 'diabetic complications', HLT 'diabetes mellitus', HLT 'carbohydrate tolerance analyses (incl diabetes)' excluding PT 'Blood glucose decreased', and including PT 'hyperglycemia'.

# 2.4.5.1 Analyses of adverse events

#### **Generalities**

The primary focus of AE reporting will be on TEAEs. Post-treatment AEs will be described separately.

If an AE date/time of onset (occurrence, worsening, or becoming serious) is incomplete, an imputation algorithm will be used to classify the AE as pre-treatment, treatment-emergent, or post-treatment. The algorithm for imputing date/time of onset will be conservative and will classify an AE as treatment-emergent unless there is definitive information to determine it is pre-treatment or post-treatment. Details on classification of AEs with missing or partial onset dates are provided in Section 2.5.1.

Adverse event incidence tables will present the number (n) and percentage (%) of patients experiencing an AE by SOC, HLGT (when applicable), HLT (when applicable), and PT. Multiple occurrences of the same event in the same patient will be counted only once in the tables within a treatment phase. The denominator for computation of percentages is the safety population.

Sorting within tables ensures the same presentation for the set of all AEs within the observation period (TEAE, and post-treatment). For that purpose, the table of all TEAEs presented by SOC and PT sorted by the internationally agreed SOC order and decreasing frequency of PTs within SOCs will define the presentation order for all other tables by SOC and PT, unless otherwise specified. The tables of AEs by SOC, HLGT, HLT and PT will be sorted by the SOC internationally agreed order and the other levels (HLGT, HLT, PT) will be presented in alphabetical order, unless otherwise specified.

#### Analysis of all treatment-emergent adverse events

The following TEAE summaries will be generated:

- Overview of TEAEs, summarizing number (%) of patients with any
  - TEAE;
  - Serious TEAE;
  - TEAE leading to death;
  - TEAE leading to permanent treatment discontinuation.
- All TEAEs by primary SOC, HLGT, HLT, and PT
- Number (%) of patients experiencing common TEAE(s) presented by primary SOC, HLT and PT (HLT incidence ≥2 % in overall patients in the OLE), sorted by SOC internationally agreed order and by alphabetic order for the other levels (HLT and PT);
- All TEAEs by primary SOC and PT, sorted by the internationally agreed SOC order and by decreasing incidence of PTs within each SOC. This sorting order will be applied to all other tables by SOC and PT of TEAEs, unless otherwise specified;
- All TEAEs regardless of relationship in one column and, in the same table a second column with TEAEs related to alirocumab according to investigator's opinion by primary SOC, HLGT, HLT and PT;
- All TEAEs by maximal intensity (ie, mild, moderate or severe), presented by primary SOC and PT, sorted by the sorting order defined above;
- The event rate per patient-year (the number of patients with an event in question divided by total patient-years in OLE study) will be provided for all TEAEs by SOC and PT. For a patient with event, patient year is censored at time of first event in OLE; for patient without event, it corresponds to length of OLE TEAE period;
- Kaplan-Meier curves will be provided, when appropriate, for time from first dose of OLE study treatment to the first occurrence of selected TEAEs as well as incidence rates at 24, 52, 78, 104 and 156 weeks of exposure. Patients without any event will be censored at the end of the TEAE period. Selected TEAEs could be local injection site reactions, general allergic reactions, hepatic disorders, diabetes among non-diabetic patients at baseline, and TEAE related to any clinically significant signal that needs further characterization.

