9 ASSESSMENT OF INVESTIGATIONAL MEDICINAL PRODUCT

9.1 PRIMARY SAFETY ENDPOINTS

The safety parameters (adverse events, laboratory data, vital signs) will be assessed throughout the study.

The definition and reporting procedures of Adverse Events (AE), Adverse Events of Special Interest (AESI) and Serious Adverse Events (SAE) and management of specific laboratory abnormalities are described in sections 10.4 to 10.6.

Adverse event observation period:

The observation of safety data will be as follows:

- Pre-treatment observation period is defined as the time from signing the informed consent to the time of first dose of alirocumab in the current study. The adverse events occurring during this period will be reported and recorded in the parent study data base.
- TEAE period: the TEAE (Treatment Emergent Adverse Event) observation period is defined as the time from first dose of alirocumab in the OLE up to 70 days (10 weeks) after the last dose of alirocumab received in the OLE study for the patients who will either complete the study or who will prematurely discontinue, as residual effect of treatment is expected until 10 weeks after the stop of alirocumab.
- Post-treatment period: the post-treatment observation period is defined as the time starting the day after the end of the TEAE period up to the end of the study (see definition in section 6.2.1).

Death observation period:

The death observations are per the observation period defined above. In addition, "post-study" death includes all deaths reported after the end of the study (see definition of end of study period per patient in Section 6.2.1).

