### Observation period

The period of safety observation starts from the time when the patient gives informed consent and is divided into the following periods:

- The PRE-TREATMENT period: defined as the time from the signed informed consent date up to the time of first dose of alirocumab in the OLE study. The adverse events occurring during this period were to be reported and recorded in the parent study database. However, after the lock of parent study database, some exceptional pre-treatment adverse events have been recorded in the OLE study database with a start date in the parent study period.
- The treatment-emergent adverse event (TEAE) period: defined as the time from the first dose of alirocumab in the OLE study up to the day of last dose of alirocumab received in the OLE study + 70 days (10 weeks), as residual effect of alirocumab is expected until 10 weeks after the stop of alirocumab.

The TEAE period will include:

- The TREATMENT period defined as the time from the first dose of alirocumab in the OLE study up to the day of last dose of alirocumab received in the OLE study + 21 days.
- The POST-TREATMENT period: defined as the time starting the day after the end of TEAE period up to the end of study

The on-study observation period is defined as the time from first dose of alirocumab in the OLE study until the last protocol planned visit of the patient in the OLE study. The last protocol planned visit is defined as the safety follow-up call if done, else 10 weeks after last injection of alirocumab.

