### Analysis of all treatment emergent serious adverse event(s)

- All serious TEAEs by primary SOC, HLGT, HLT, and PT and by SOC/PT;
- All serious TEAEs regardless of relationship in one column and, in the same table a second column with TEAEs related to alirocumab according to investigator's opinion, by primary SOC, HLGT, HLT, and PT;
- The event rate per patient-year will be provided for all serious TEAEs by SOC and PT.

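### TEAE patient-year rates and Kaplan-Meier censoring run to last dose + 70 days and do not stop at death, last contact or, for patients past their EOT visit, an interim cut-off, so rates come out slightly too low

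*SAP*

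**What the plan says.** SAP 2.1.4 (Observation period) ends the TEAE period at "last dose of alirocumab received in the OLE study + 70 days (10 weeks), as residual effect of alirocumab is expected until 10 weeks" after treatment stops. Protocol 9.1 agrees: "up to 70 days (10 weeks) after the last dose of alirocumab received in the OLE study". The reason given is residual drug effect, not how long the patient was observed.

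SAP 2.4.5.1 uses this period in two ways:

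- **Patient-year rates.** Time stops at the first event for a patient who has one; "for patient without event, it corresponds to length of OLE TEAE period". The same measure is planned for serious events: "The event rate per patient-year will be provided for all serious TEAEs by SOC and PT".
- **Kaplan-Meier analyses of selected TEAEs.** "Patients without any event will be censored at the end of the TEAE period". Protocol 11.4.2.1 has the same censoring rule.

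SAP 3 adds an interim rule. Patients with no EOT visit by the cut-off count as ongoing, and their TEAE period ends at the cut-off. AEs that start, worsen or become serious after the cut-off are left out for everyone.

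**The concern.** Time at risk should be time in which an event would be seen and counted. A period fixed at last dose + 70 days meets that condition only if the patient is alive and in contact throughout. A patient who dies soon after the last dose stops contributing to the fatal term at its onset, but stays at risk after death for every other SOC and PT. A patient with no contact after the last dose contributes 70 event-free days that nobody observed.

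The error can only lengthen time at risk, so patient-year rates can only be too low. The primary objective is long-term safety, so even a small error in the reassuring direction deserves removal if that is cheap.

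**Working it through.** **1. Does any other rule supply the cap?**

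- SAP 2.5.3 uses the date of last contact, but only to impute a missing last-injection date. The 70 days are still added.
- SAP 2.2 foresees patients who died before the call, had no call, or were called before 9 weeks. It uses this only to report insufficient follow-up in the disposition summary.
- SAP 3 cuts the TEAE period only for patients still ongoing at an interim.
- SAP 2.4.5.3 and 2.4.5.4 censor Kaplan-Meier analyses of potentially clinically significant abnormalities (PCSAs) at the last assessment performed. For TEAEs the text differs, so a programmer following it would code last dose + 70 days for all.

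None of these caps the TEAE period at death or last contact.

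**2. Unobserved days per patient**

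- Death or no contact straight after the last dose: up to 70 days, or 70/365.25 = 0.19 patient-years.
- Completer who misses only the call: the EOT visit is 2 weeks after the last injection (SAP 1.4), so 70 - 14 = 56 days.
- Completer whose EOT visit falls on an interim cut-off date: the period runs 70 - 14 = 56 days past it, and AEs in those days are excluded.

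Share of one patient's TEAE period that is tail, with the last dose at week w: 70 / (7w + 71).

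| Last dose | TEAE days | Tail share |
|---|---|---|
| Day 1 only | 71 | 98.6% |
| Week 22 | 225 | 31.1% |
| Week 50 | 421 | 16.6% |
| Week 102 | 785 | 8.9% |
| Week 166 | 1,233 | 5.7% |

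The effect is concentrated in early deaths and early dropouts.

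**3. Effect on rates**

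The documents give no dropout, exposure or event figures, so there is no stated figure to reproduce and the inputs are assumptions: share of patients affected f = 1-10%, unobserved days each u = 35-70, mean TEAE period L = 52-176 weeks. The upper limit of L corresponds to a last dose at week 166 plus 70 days.

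Understatement of the rate: s = f × u / L. Rise after correction: s / (1 - s).

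- Smallest: 0.01 × 35 / 1,232 = 0.03%.
- Middle (f = 5%, u = 70, L = 130 weeks = 910 days): 3.5 / 910 = 0.38%; rise 0.39%.
- Largest (f = 10%, u = 70, L = 52 weeks = 364 days): 7 / 364 = 1.9%; rise 2.0%.

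For the middle case with 1,200 patients, total time is 1,200 × 910 / 365.25 = 2,990 patient-years, of which 60 × 70 / 365.25 = 11.5 are unobserved. With 60 patients having an event, and ignoring their earlier stop at that event, the rate moves from 2.007 to 2.015 per 100 patient-years.

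**4. Which outputs are affected?**

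- Affected: patient-year rates for TEAEs and serious TEAEs, and Kaplan-Meier analyses of selected TEAEs. A Kaplan-Meier estimate falls only if another patient's event occurs while the unobserved patient is still in the risk set; otherwise it is unchanged.
- Not affected: AE percentages, whose denominator is the safety population (SAP 2.4.5.1), and the PCSA Kaplan-Meier analyses.

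**The case against.** The strongest reply is that this is immaterial. The main AE tables give numbers and percentages of patients. Patient-year rates are a single item in each of two lists, and Kaplan-Meier curves are planned only where appropriate. The study is uncontrolled and its safety analysis descriptive. All of this stands, and it limits the point to a correction of secondary outputs. A reader might infer that the denominator of the whole primary safety analysis is wrong; the safety-population denominator rules that out.

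A second reply is that a missed call does not mean that no event could be recorded. Protocol 10.3.4 requires at least 10 weeks of follow-up after early discontinuation, 10.3.5 asks for best efforts to establish health status, and related SAEs learned of later are still reported (10.4.3). This also stands: some tails will be partly observed, so 70 days is a ceiling. It does not help for time after death, after a last contact that could not be extended, or after an interim cut-off.

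A third concerns Kaplan-Meier. Censoring at death treats a competing event as non-informative and can overstate cumulative incidence. That is fair, so the argument is cleanest for patient-year rates. But keeping a deceased patient in the risk set for up to 70 days is not a planned competing-risk method either.

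Finally, SAP 2.1.4 sets the last planned visit, "defined as the safety follow-up call if done, else 10 weeks after last injection of alirocumab". A reader might take this as the person-time rule. It defines the on-study period, which is used to classify deaths, and does not set TEAE time at risk.

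**Conclusion.** The point holds for patient-year rates of TEAEs and serious TEAEs and for Kaplan-Meier analyses of selected TEAEs. Read literally, the plan counts up to 70 unobserved days per event-free patient. It is clearest at an interim: the plan excludes AEs after the cut-off, yet it leaves in the time after the cut-off for patients whose EOT visit was done but whose last dose was less than 70 days earlier. It would be wrong to infer that interims are unprotected altogether, because ongoing patients are already cut at the cut-off.

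Rates are understated by about 0.03-2% on the assumed inputs; Kaplan-Meier incidence is lower or unchanged. The assumption most open to doubt is the share affected at an interim. Patients complete when the drug becomes available in their country (Protocol 6.2.1), so completions may cluster and exceed 10%. The conclusions of the study are unlikely to change. This is a minor correction.

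**What to change.** Add to SAP 2.4.5.1 that, for TEAE person-time and Kaplan-Meier censoring only, time at risk ends at the earliest of last dose + 70 days, death, last contact and, at an interim, the cut-off date for all patients. Carry the cut-off part into SAP 3. Leave the TEAE period itself, and so the classification of AEs as treatment-emergent, unchanged.

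The Kaplan-Meier part departs from Protocol 11.4.2.1, so record it in SAP 1.6, which now reports no modifications. No new data are needed: last contact is already used in SAP 2.5.3, and deaths are already summarised by study period. The cost is a sentence or two, the SAP 1.6 entry and slightly less favourable rates. If the team is concerned about death as a competing event, it can say in the same place how the Kaplan-Meier results should be read.

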### Analysis of all treatment emergent serious adverse event(s)

- All serious TEAEs by primary SOC, HLGT, HLT, and PT and by SOC/PT;
- All serious TEAEs regardless of relationship in one column and, in the same table a second column with TEAEs related to alirocumab according to investigator's opinion, by primary SOC, HLGT, HLT, and PT;
- The event rate per patient-year will be provided for all serious TEAEs by SOC and PT.

# Analysis of all treatment-emergent adverse event(s) leading to treatment discontinuation

• All TEAEs leading to treatment discontinuation, by primary SOC, HLGT, HLT, and PT.

# Analysis of groupings of adverse events including selected adverse events of special interest

All grouping of TEAEs including adverse events of special interest as listed in Section 2.1.4.1 will be analyzed using selections defined in Section 2.1.4.1 and will be presented by SMQ and PT (when selection is based on SMQs) and by SOC and PT (when selection is based on the e-CRF tick box or HLGT/HLT). The summaries will be sorted by decreasing incidence of PT within each SOC/SMQ.

- Analyses of grouping of AEs for diabetes will be performed overall and according to the diabetic status at baseline.
- Serious TEAEs by PT for each grouping of AEs of special interest;
- TEAE(s) leading to permanent treatment discontinuation by PT for each grouping of AEs of special interest.

In addition, the following variables will be tabulated for the local injection site reactions TEAEs:

- Intensity of the event (mild, moderate, severe);
- Number of events divided by the number of OLE IMP injections received;
- Time from first OLE IMP injection to first injection site reaction;
- Description of the highest intensity of each symptom recorded in the specific e-CRF page with table and bar chart.

Besides, description of symptoms and possible etiologies for General Allergic Reaction TEAE reported by investigator (using the tick box), will be presented.

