6.2 DURATION OF STUDY PARTICIPATION

6.2.1 Duration of study participation for each patient

The OLE study is planned to be completed in second quarter 2017 which corresponds to a study duration of approximately 168 weeks for the first patients enrolled or until the drug is commercially available for the patient in the respective country, whatever comes first. For patients in the UK, the study will last a maximum of 176 weeks.

The study duration includes up to approximately 3.5 years of treatment for the first patients enrolled, and 10 weeks of follow up after the last IMP injection for all the patients, those who will complete the study and those who will early discontinue whatever the reason.

The study will be considered as completed for a patient in the following situations:

- When the alirocumab is commercially available in the patient's country
- In second quarter 2017, if alirocumab is not yet commercially available in the patient's country

An EOT visit will be done 2 weeks after the last IMP injection and a safety follow up call 10 weeks after the last IMP injection.

The following situations will be considered as premature discontinuation of the patient from the study:

- Any withdrawal from the study to switch to an anti-PCSK9 inhibitor different from commercial alirocumab
- Any other reason

An unscheduled visit should take place within 5 days after the last IMP administration if possible, with assessments normally planned at the EOT visit, and a safety follow up call performed 10 weeks after the last IMP injection (see section 10.3.4).

The end of study per patient is the last protocol planned call. Patients with a Serious Adverse Events (SAEs) or an Adverse Event of Special Interest (AESI) should be followed until resolution, stabilization, or death.

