10.1.1.17 End-of-treatment visit: Visit 17/ Week 168/ Month 40 (Day 1177± 7)

The end of study is scheduled to be in second quarter 2017 or when the drug will become commercially available for the patient in the respective country whatever comes first. Thus, the End-of-treatment visit might be performed earlier than on Week 168 according to the date of inclusion of each patient in the OLE study, or if the patient early discontinues the study.

- Collect adverse events
- Record concomitant medication
- Take vital signs including heart rate and blood pressure
- Get body weight measurement
- Physical examination
- Review patient's diet. Patient should be on a NCEP-ATPIII TLC diet or equivalent.
- Data collection on IMP administration and IMP compliance check by review of diary and treatment kit
- IVRS/IWRS contact to document the end of treatment
- Obtain fasting blood sample for:
 - Lipids: measure and/or calculation of total-C, LDL-C, HDL-C, TG, non-HDL-C, Apo B, Apo A-1, ratio Apo B/Apo A-1, and Lp (a)

- Hematology
- Chemistry
- CPK
- Liver panel
- Anti-alirocumab antibodies

- Local urine pregnancy test (females of childbearing potential only).
- Completion of EQ-5D questionnaire by patient.
- Reminders
 - For all the patients, those who prematurely discontinue the treatment irrespective of the reason and those who will complete the study, an appointment will be given for the Follow up call. This phone call will have to be scheduled 10 weeks after last injection (+/- 7 days).

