# 1 OVERVIEW AND INVESTIGATIONAL PLAN

#### 1.1 STUDY DESIGN AND RANDOMIZATION

This is a Phase 3, multicenter, multinational, open-label extension (OLE), uncontrolled study that includes patients diagnosed with heterozygous familial hypercholesterolemia (heFH) who have completed one of the four randomized, double-blind, 18-month parent studies: EFC12492 (ODYSSEY FH I), R727-CL-1112 (ODYSSEY FH II), EFC12732 (ODYSSEY High-FH) or LTS11717 (ODYSSEY long term).

The first study visit (Visit 1 on Day 1) of the OLE study takes place at the end of treatment (EOT) visit for patients enrolled in EFC12492, R727-CL-1112 and EFC12732 studies, or at the end of study (EOS) visit for those enrolled in the LTS11717 study.

All patients receive alirocumab 75 mg every 2 weeks (Q2W) at entry into the OLE, with the exception of patients from EFC12732 who receive 150 mg Q2W, as in the parent study. From Day 1 (Visit 1) to Week 8 (first unblinded LDL-C value), neither the treatment received at the end of double-blind treatment period of the parent study, nor the lipid parameters level, will be known by the investigator or by the patient, in order to prevent any potential blinding breaking of the parent study. From Week 12 (Visit 4), the investigator may manage adjustment of alirocumab doses (uptitration from 75 mg to 150 mg Q2W, down-titration from 150 mg to 75 mg Q2W or maintenance of dose), based on his/her own judgment and LDL-C values. Patients are to be treated for up to 168 weeks ie approximately 3.5 years with alirocumab, for the first patients enrolled, or until the product becomes commercially available for the patient in the country, whatever comes first. All patients are to be followed by phone 10 weeks after last investigational medicinal product (IMP). Patients with a Serious Adverse Events (SAEs) and or an Adverse Event of Special Interest (AESI) should be followed until resolution, stabilization, or death.

Up to approximately 1,200 heFH patients were estimated to be enrolled from approximately 200 sites worldwide.

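### Apart from injection site reactions, the special-interest event groupings, and deaths, have no committed exposure-adjusted estimate although follow-up ends at country launch, and no safety result has a confidence interval

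*SAP*

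**What the plan says.** **Follow-up.** SAP 1.1 plans treatment for up to 168 weeks or "until the product becomes commercially available for the patient in the country, whatever comes first". Protocol 6.2.1 counts a patient as having completed the study "When the alirocumab is commercially available in the patient's country", and otherwise in the second quarter of 2017. Protocol 10.1.1.17 adds that the end-of-treatment visit "might be performed earlier than on Week 168 according to the date of inclusion of each patient in the OLE study".

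**Percentages.** SAP 2.4.5.1 (Generalities) states: "The denominator for computation of percentages is the safety population".

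**Where a patient-year rate is committed.** SAP 2.4.5.1 defines it as patients with the event over total patient-years, with time cut at the first event or at the end of the TEAE period. It applies this to all TEAEs by SOC and PT, and then: "The event rate per patient-year will be provided for all serious TEAEs by SOC and PT".

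**Where it is not.**
- For the groupings: "All grouping of TEAEs including adverse events of special interest as listed in Section 2.1.4.1 will be analyzed using selections defined in Section 2.1.4.1", shown by SMQ and PT or by SOC and PT.
- For discontinuations: "All TEAEs leading to treatment discontinuation, by primary SOC, HLGT, HLT, and PT".
- For deaths, SAP 2.4.5.2 gives number and percentage by study period.

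**Other measures that allow for exposure.**
- SAP 2.2 commits, without condition, to a Kaplan-Meier graph of premature treatment discontinuation due to AEs.
- Injection site reactions get events per injection and time to first reaction (SAP 2.4.5.1).
- General allergic, hepatic and diabetes events are named as possible subjects for Kaplan-Meier curves, in conditional wording (SAP 2.4.5.1).
- The ALT increase is summarized with the PCSAs. Kaplan-Meier for selected PCSAs follows only if a signal is detected (SAP 2.4.5.3).

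**Intervals.** Confidence intervals are planned for efficacy results only (Protocol summary and 11.4.3; SAP 2.4.4.2).

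**The concern.** When follow-up ends at different times for administrative reasons, a crude percentage reflects both the risk and the time observed. Here that time depends partly on launch dates and enrolment dates, which say nothing about the drug. The sponsor sees the issue: Protocol 11.4.2.1 offers time-to-event work because exposure differs between patients. The SAP also has a suitable rate, but does not commit it to the groupings it singles out for attention or to deaths.

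At stake is how the targeted safety results can be read. A group percentage can differ between an interim and the final analysis, or from the 18-month parent studies, through follow-up alone. For rare groups, a percentage without an interval does not show what risk remains compatible with the data.

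**Working it through.** **1. Expected size.** No power calculation exists. The heFH patients in the parent-study table (Protocol section 4) sum to 486 + 249 + 107 + 385 = 1,227, against the stated figure of about 1,200. The difference is 27/1,200 = 2.25%, so the planned number reproduces.

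**2. What is committed, by event type.**

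| Event | Committed at group level | Conditional |
|---|---|---|
| Neurologic, neurocognitive, ophthalmologic, hemolytic anemia | n (%) | Kaplan-Meier if a signal appears |
| Deaths | n (%) | none stated |
| ALT increase | n (%), PCSA denominator of patients assessed (SAP 2.4.5) | Kaplan-Meier if a signal appears |
| General allergic, hepatic, diabetes | n (%) | named Kaplan-Meier candidates |
| Injection site reactions | n (%), events per injection, time to first reaction | named Kaplan-Meier candidate |
| Discontinuation due to AEs | n (%), Kaplan-Meier graph | none stated |

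**3. Can the PT rates be summed to a group rate?** No. A patient with memory impairment and a later confusional state counts once in the neurocognitive group, with time cut at the first event. The same patient counts in two PT rates, each with its own cut. Some selections are also not visible in a SOC/PT table: the ALT increase comes from laboratory data, hemolytic anemia needs a tick box plus a confirmed diagnosis, and one neurocognitive grouping includes LLTs (SAP 2.1.4.1).

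**4. Effect of follow-up on a crude percentage.** Assume a constant rate r per patient-year and risk time of T years. The crude proportion is 1 − exp(−rT), with T = weeks × 7/365.25. The rates and stopping times are assumptions.
- r = 0.01: 0.46% at 24 weeks, 0.99% at 52 and 3.17% at 168.
- r = 0.02: 1.97% at 52 weeks and 6.24% at 168; 4.10% if half the patients stop at each.
- r = 0.05: 4.86%, 14.87% and 9.87% respectively.
- r = 0.01 in a mixture: with 25% stopping at 52 weeks and 75% at 168, 0.25 × 0.99 + 0.75 × 3.17 = 2.62%. With the shares reversed, 1.54%.

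The TEAE period runs to the last dose plus 70 days. Stopping at 52 or 168 weeks therefore gives risk time to about week 60 or 176. The mixtures become about 2.77% and 1.69%, in the same direction. Events over patient-years recover r in every case.

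**5. Precision.** Exact 95% limits:
- 0 of 1,200 patients: up to 0.31%. 12 of 1,200 (1.0%): 0.52% to 1.74%.
- 12 events in an assumed 1,200, 2,400 or 3,600 patient-years: 1.00 (0.52 to 1.75), 0.50 (0.26 to 0.87) or 0.33 (0.17 to 0.58) per 100 patient-years.
- 0 events over the same patient-years: upper limits of 0.31, 0.15 and 0.10 per 100.

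For scale, 1,200 patients all reaching week 168 would give 1,200 × 3.22, or about 3,860 patient-years.

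**The case against.** A reader might infer that events of special interest, AE discontinuations and deaths all get nothing but crude percentages. The documents do not support that. Discontinuation due to AEs has a firm Kaplan-Meier graph, which handles administrative censoring. Injection site reactions have two exposure-based measures. Allergic, hepatic and diabetes events are named Kaplan-Meier candidates, and any signal can trigger time-to-event work. What remains is that the last two routes are optional or depend on the data, and that the graph has no stated estimates or intervals.

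It is also fair to say that a reader could approximate a missing rate. For rare events, cutting time at the first event barely changes the total, so the group count over N times mean exposure comes close. However, the planned exposure (SAP 2.4.3.1) ends at last injection plus 14 days, while the TEAE period runs to plus 70, so the reader would have to add 56 days per patient. An exact interval for n/N can also be worked out by hand. This limits the harm but does not justify leaving the calculation to the reader.

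A further tempting inference is that launch timing distorts the comparison by parent treatment. That treatment was randomized, so launch timing should be broadly similar across the split. The problem mainly concerns absolute levels. Nor is all comparison between interim and final analysis lost, since PT rates and any fixed-time Kaplan-Meier estimates remain comparable.

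Finally, omitting intervals from a descriptive, uncontrolled study contradicts nothing in the documents. But the SAP gives intervals for lipid means that are not tested either, so the descriptive design is no reason to leave them off the primary objective.

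**Conclusion.** The point stands as a recommended change. Followed as written, the SAP yields group-level percentages that move with launch and enrolment timing at constant risk, for neurologic, neurocognitive, ophthalmologic and hemolytic anemia events, for deaths and, unless a signal appears, for the ALT increase. For allergic, hepatic and diabetes events, a remedy is possible but not committed. No safety estimate carries an interval.

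The illustrated swing is roughly threefold between risk time ending at 52 and at 168 weeks. It rests on an assumed constant hazard and assumed stopping times. The documents give no launch dates, minimum follow-up, event rates or total patient-years, so the actual size in this study cannot be stated.

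**What to change.** In SAP 2.4.5.1 and 2.4.5.2:

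- Apply the existing patient-year definition to each grouping in SAP 2.1.4.1, with one rate per group and time cut at the first event of that group.
- For the laboratory-based ALT increase, count time to the first qualifying value, or to the last assessment in the TEAE period.
- Do the same for deaths.
- Present these rates overall and by parent treatment, with exact Poisson 95% intervals. Add the same intervals to the rates already planned, and keep n (%) beside them.
- For discontinuation due to AEs, add numerical Kaplan-Meier estimates with 95% intervals at 24, 52, 78, 104 and 156 weeks, the time points the SAP already uses, to the curve planned in SAP 2.2.

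The cost is SAP wording and a few table columns, with no new data collection. The downside is visibly wide intervals for rare events.
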